7.3.3 Follow up study visits

Follow-up Visit (Day 7) Visit 3 (+/- 1 day)

- Medical History, Vital Signs, Physical Examination, Head Lice Visual Assessment, Local Skin/Scalp Irritation, Assessment, Ocular Irritation Assessment.
- Record results on Source Document.
- Record adverse events as reported by participant or observed by investigator.
- Record subject's adherence to homecare instructions.
- Perform assessment for living head lice on subject for visual confirmation of infestation.
- Record subject's adherence to homecare instructions.
- If, at day 7, live lice are still present, a repeat treatment will be administered followed by thorough combing
- Inform each subject when to come back for their Final visit (Day 14) Visit 4 +2 days.

7.3.4 Final study visits

Visit Day 14 (Visit 4) (+/- 2 days)

- Medical History, Physical Examination, Vital Signs, Urine Pregnancy Test, Head Lice Visual Assessment, Local Skin/Scalp Irritation Assessment, Ocular Irritation Assessment,
- Concomitant and Prohibited Medication Review and record results on Source Document.
- Record adverse events as reported by participant or observed by investigator.
- Perform assessment for living head lice on subject for visual confirmation of infestation for a minimum of 15 minutes.
- If, after day 14, a subject reports clear signs of infestation i.e., the presence of live lice, they will be regarded as a treatment failure and they will be offered treatment with an alternative product, Vamousse Mousse.

7.3.5 Unscheduled visit

Subjects will be encouraged to report any complications or adverse effects during their participation. Investigator may evaluate the subject at an unscheduled visit, if subject's condition is considered to be worsening.

7.3.6 Rescreening

If for some reason a subject is approved to participate in the study, but cannot return to the clinical site within 24 hours of their screening visit, they may be rescreened within 1 week. This rescreening may also occur if all household members cannot be assessed at the clinical site within 24 hours of the subject's approval to participate in the study. Rescreening will be considered on an individual subject basis and must first be approved by the Investigator or Medical Monitor.

7.4 Concomitant/precautionary medication, treatment and procedures

As part of standard medical history, all medications (both prescription and nonprescription, and including vitamins, herbals, topical, inhaled, and intranasal) taken within 30 days prior to the start of the Study Drug and through the final study visit will be recorded on the appropriate source document (using their generic and brand names, if known) with the corresponding indication, start and stop dates. At each study visit, subjects will be asked whether they have started or discontinued any medication since their previous study visit. This includes single use or PRN (as needed) medication use.

Previous treatment of head lice must be recorded irrespective of the term it was given. Corresponding condition shall be captured in the subject's Medical History.

7.5 Prohibited medication, treatment and procedures

Head lice treatment products (over the counter [OTC], home remedy and/or Prescription) are prohibited 30 days prior to and during the study. These include, but are not limited to:

- Nix Ultra
- Rid Max
- LiceMD

7.6 Rescue medication, treatment and procedures

If live lice are present on Day 14, the subject will receive the over-the-counter (OTC) rescue treatment, Vamousse Mousse, for head lice and their study participation will be considered complete and will be considered a treatment failure.

7.7 Participant access to study product at study center

Participants will receive the study product at their Enrollment/Baseline Visit/ Day 0.

8. Assessment of Safety

8.1 Specification of study parameters

The Investigator will monitor each subject for clinical evidence of adverse events on a routine basis throughout the study. The Investigator will assess and record any AE in detail including the date of onset, description, severity, time course, duration and outcome, relationship of the adverse event to study drug, an alternate etiology for events not considered "related" or "probably related" to study drug, final diagnosis, if known, and any action(s) taken. For AEs to be considered intermittent, the events must be of similar nature and severity and each intermittent AE will be reported separately. AEs and SAEs, whether in response to a query, observed by site personnel, or reported spontaneously by the subject will be recorded, monitored and followed-up until the resolution (or until the Investigator deems the event to be stable/chronic).

8.1.1 Definition of adverse events (AE)

An AE is defined as any untoward medical occurrence in a patient or clinical investigation subject administered a pharmaceutical product and which does not necessarily have a causal relationship with this treatment. An AE can therefore be any unfavorable and unintended sign (including an abnormal laboratory finding), symptom, or disease temporally associated with the use of a medicinal (investigational) product, whether or not the event is considered causally related to the use of the investigational product. Treatment-emergent AEs (TEAE) will include any AEs reported beginning with the application of study drug on Day 0.

Such an event can result from use of the drug as stipulated in the protocol or labeling, as well as from accidental or intentional overdose, drug abuse, or drug withdrawal. Any worsening of a pre-existing condition or illness is considered an AE. I.e., if a new signs or symptom or worsening of a sign or symptom was believed by the investigator to be related to the study drug and not the disease, then it was recorded as an AE. Clinically significant abnormalities are to be followed to resolution (i.e. become stable, return to normal, return to baseline, or become explainable). Changes in vital signs are considered to be AEs only if they necessitate therapeutic medical intervention, and/or if the Investigator considers them to be AEs.

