Study Objectives	
The primary objective of the study will explore whether treatment with Vamousse Spray 'n' Go is more effective in killing lice & eggs compared to a permethrin-based control product.
 
The secondary objective of the study is to demonstrate the safety and local tolerability of Vamousse Spray 'n' Go in children 2yo+.

Study Endpoints	
The primary efficacy endpoint is the proportion of subjects who are lice free (defined as no live lice, adults or nymphs) 14 days after treatment.
 
The secondary efficacy endpoint is the number and percentage of all subjects who are lice-free at Day 2.

Number of Subjects and Site	The planned overall sample size for this Open-Label Clinical Trial is approximately 58 subjects to be enrolled at clinical research center in the United States, specifically Miami, FL. The subjects will be evenly divided between the Spray 'N' Go treatment group and the permethrin control group (29 subjects in each).
Eligibility Criteria	Subjects who satisfy ALL the inclusion criteria and have NONE of the exclusion criteria may be enrolled in the study.

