8.2.2 Relationship to study product

The Investigator will use the following definitions to assess the relationship of the AE/SAE to the use of investigational product:

Definitely Related	The event occurred within a reasonable time after drug administration or drug concentration and body fluids demonstrated that the study drug was present: the event could not be reasonably explained by known characteristics including concomitant therapies; the adverse event abated after discontinuing the study drug.
Probably Related	The event has a strong temporal relationship to study drug or recurs on re-challenge and another etiology is unlikely or significantly less likely.
Possibly Related	The event has a strong temporal relationship to the study drug and an alternative etiology is equally or less likely compared to the potential relationship to study drug.
Probably Not Related	The event has little or no temporal relationship to the study drug and/or a more likely alternative etiology exists.
Not Related	The event is due to an underlying or concurrent illness or effect of another drug and is not related to the study drug (e.g., has no temporal relationship to study drug or has a much more likely alternative etiology).

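### Section 8.1.1 contradicts its own AE definition: one sentence can be read as recording a new or worsening sign only when the investigator blames the drug and not the infestation

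*Combined protocol and SAP*

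**What the plan says.** Section 8.1.1 of the combined protocol and SAP opens with a definition that does not depend on cause. An AE is an untoward occurrence "which does not necessarily have a causal relationship with this treatment", and a sign, symptom or disease counts "whether or not the event is considered causally related to the use of the investigational product". The second paragraph adds, without any causality condition, "Any worsening of a pre-existing condition or illness is considered an AE".

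The next sentence begins with 'I.e.' and so presents itself as the meaning of what precedes it. It says that if a new or worsening finding "was believed by the investigator to be related to the study drug and not the disease, then it was recorded as an AE".

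Elsewhere the plan treats AEs as a set that includes unrelated events:

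- Section 8.1: "The Investigator will assess and record any AE in detail". The detail required includes another cause for events not judged related.
- Section 8.2.2: the relationship scale includes Probably Not Related and Not Related, the latter defined as "The event is due to an underlying or concurrent illness or effect of another drug and is not related to the study drug".
- Section 10.4.3: treatment-emergent AEs (TEAEs) are tabulated by group, with a separate summary of those related to study drug.

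The synopsis states the setting: "The planned overall sample size for this Open-Label Clinical Trial is approximately 58 subjects". The documents describe no blinded assessor of AEs.

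**The concern.** The sentence asks the investigator to separate drug from disease, and local scalp signs are where that is hardest. Section 7.1.1 has subjects examined for pruritus, erythema, excoriation and pyoderma. Section 2.3.1 lists irritation, allergic skin reaction, dryness and cracking as possible effects of the test product. Exclusion 3 of the synopsis accepts that some scalp conditions are attributable to the infestation itself. The person making the judgement knows the arm.

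If relatedness decides whether an event is recorded, the AE tables hold only what the investigator already believed was caused by the product. Safety and local tolerability in children from age 2 is the secondary objective. Section 4.2.3 judges product safety by reported AEs, and 10.4.3 names AEs as the safety variables. An event never entered as an AE cannot be put back into those tables at analysis.

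**Working it through.** The plan states no AE rate, so there is no figure to reproduce. The main check is to follow one event through the text.

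**Step 1: one event, each rule.** Take scalp redness present at baseline that is worse at Day 2, which the investigator puts down to the lice.

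| Text | What happens to the event |
|---|---|
| 8.1.1, definition | AE; cause does not matter |
| 8.1.1, worsening sentence | AE |
| 8.1.1, 'I.e.' sentence | Fails the stated condition; on the natural reading, not recorded |
| 8.1 | Recorded, with the other cause noted |
| 8.2.2 | Graded Not Related or Probably Not Related |
| 10.4.3 | In the all-TEAE table, not in the related-TEAE table |

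Five of the six agree. The 'I.e.' sentence would keep the event from ever reaching the grade that 8.2.2 provides for it. It would also tend to make the two TEAE summaries in 10.4.3 the same.

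**Step 2: what the filter could do to counts (illustration).** Expected recorded AEs in an arm = n × t × a, where n = 29 (synopsis and 10.5), t = true proportion with a new or worsening scalp sign, and a = proportion of those signs attributed to the drug. Both t and a are assumptions; the documents give neither.

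Same true rate in both arms, with a = 0.80 in one and 0.40 in the other:

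| t | Arm with a = 0.80 | Arm with a = 0.40 | Spurious gap |
|---|---|---|---|
| 20% | 29 × 0.20 × 0.80 = 4.6 | 29 × 0.20 × 0.40 = 2.3 | 8 points |
| 30% | 29 × 0.30 × 0.80 = 7.0 | 29 × 0.30 × 0.40 = 3.5 | 12 points |
| 40% | 29 × 0.40 × 0.80 = 9.3 | 29 × 0.40 × 0.40 = 4.6 | 16 points |

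Reversing the attribution reverses the sign. With a = 0.50 in both arms there is no gap, but half the events are lost. A real difference can also vanish: 40% versus 20% with a = 0.50 versus 1.00 gives 29 × 0.40 × 0.50 = 5.8 and 29 × 0.20 × 1.00 = 5.8.

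**Step 3: sensitivity of a planned summary.** The synopsis describes severity and duration only for AEs in at least 5% of subjects. If all 58 are treated, 0.05 × 58 = 2.9, so three subjects are needed (3/58 = 5.2%; 2/58 = 3.4%). One unrecorded event can therefore drop a term from that summary.

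**The case against.** The strongest reply is that the sentence says 'if', not 'only if', and that the working instructions for recording lie elsewhere and carry no filter. Section 8.1 calls for any AE to be recorded. Sections 7.3.2 to 7.3.4 call at each follow-up visit for events reported by the participant or seen by the investigator. A site that followed these would lose nothing. This stands in part: a reader might infer that 8.1.1 forbids recording unrelated events, or that this sentence overrides the rest, and the text does not go so far. But 'I.e.' offers the sentence as the meaning of the rule, so site staff could reasonably apply it as the test.

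Second, local signs are captured by other routes. Section 16.1 schedules scalp and ocular irritation assessments at all four visits. Subjects or caregivers score itching and stinging/burning with no attribution step (16.4), and the synopsis plans a between-group analysis of those scores. Section 10 puts all collected data in listings. This stands, so a reader should not infer that the information leaves the trial altogether. The gap is narrower: no analysis outside the AE tables is stated for erythema, excoriation, pyoderma or the ocular findings.

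Third, serious AEs are reportable whether or not related (8.4.4.1), and the safety analysis is descriptive, with no formal test to distort. Both are correct.

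Fourth, keeping signs of infestation out of the AE counts can be a legitimate choice, since it avoids mixing treatment failure with safety. It can be, but the section's own definition says the opposite. Under that definition a baseline sign that merely persists is not an AE; one that worsens is.

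**Conclusion.** The contradiction within 8.1.1 is certain from the text, as is the conflict with 8.1, 8.2.2 and 10.4.3. The consequence is conditional: if a site applies the sentence, non-serious AEs may be under-recorded, or recorded differently by arm, in the AE tables. A reader might infer that the safety comparison is biased. The documents do not support that as a fact, because they show neither how sites will read the sentence nor how attribution would differ between arms. Direction and size cannot be determined, and the gaps of 8 to 16 percentage points above are illustrations on assumed rates. Efficacy, serious AE reporting, the scheduled irritation assessments and the self-reported scores are not subject to the filter. This is a wrong sentence that should be corrected, not a flaw in the design.

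**What to change.** Delete the 'I.e.' sentence from 8.1.1. Recording in both arms then follows the section's causality-independent definition, and relationship, including attribution to the infestation, is graded separately under 8.2.2. Leave the existing vital-signs provision in 8.1.1 and 7.1 as it is, so that not every change in a vital sign becomes an AE.

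The cost is one deleted sentence and some more AE entries, including some that are due to the lice. The relationship grade and the separate summary of related TEAEs in 10.4.3 already distinguish those.

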8.1.2 Definition of serious adverse events (SAE)

If an AE meets any of the following criteria, it is to be reported to the Sponsor's Safety department and Pharmacovigilance as a serious adverse event (SAE) using SAE report form within 24 hours of occurrence or notification to the study site:

Death of Subject	An event that results in the death of a subject,
Life-Threatening	An event that, in the opinion of the Investigator, would have resulted in immediate fatality if medical intervention had not been taken. This does not include an event that would have been fatal if it had occurred in a more severe form.
Hospitalization	An event that results in an admission to the hospital for any length of time. This does not include an emergency room visit or admission to an out-patient facility.
Prolongation of Hospitalization	An event that occurs while the study subject is hospitalized and prolongs the subject's hospital stay.
Congenital Anomaly/birth defect	An anomaly detected at or after birth or any anomaly that result in fetal loss.
Persistent or Significant Disability/Incapacity	An event that results in a condition that substantially interferes with the activities of daily living of a study subject. Disability is not intended to include experiences of relatively minor medical significance such as headache, nausea, vomiting, diarrhea, influenza, and accidental trauma (e.g., sprained ankle).
Other Important Medical Event	An important medical event that may not be immediately life-threatening or result in death or hospitalization, but based on medical judgment may jeopardize the subject and may require medical or surgical intervention to prevent any of the outcomes listed above (i.e., death of subject, life- threatening, hospitalization, prolongation of hospitalization, congenital anomaly, or persistent or significant disability/incapacity). Examples of such events include allergic bronchospasm requiring intensive treatment in an emergency room or at home, blood dyscrasias or convulsions that do not result in inpatient hospitalization, or the development of drug dependency or drug abuse.

8.1.3 Definition of unanticipated problems

- An Unexpected Adverse Event is any AE that is not identified in nature, severity, or frequency in the current Investigator's Brochure or product information.
- A Serious and Unexpected Suspected Adverse Reaction (SUSAR) is any suspected adverse reaction to the study product that is both serious and unexpected.

8.2 Classification of an adverse event

8.2.1 Severity of event

The Investigator will use the following definitions to rate the severity of each AE and SAE:

Mild	The event is transient and easily tolerated by the subject.
Moderate	The event causes the subject discomfort and interrupts the subject's usual activities.
Severe	The event causes considerable interference with the subject's usual activities and may be incapacitating or life-threatening.

8.2.2 Relationship to study product

The Investigator will use the following definitions to assess the relationship of the AE/SAE to the use of investigational product:

Definitely Related	The event occurred within a reasonable time after drug administration or drug concentration and body fluids demonstrated that the study drug was present: the event could not be reasonably explained by known characteristics including concomitant therapies; the adverse event abated after discontinuing the study drug.
Probably Related	The event has a strong temporal relationship to study drug or recurs on re-challenge and another etiology is unlikely or significantly less likely.
Possibly Related	The event has a strong temporal relationship to the study drug and an alternative etiology is equally or less likely compared to the potential relationship to study drug.
Probably Not Related	The event has little or no temporal relationship to the study drug and/or a more likely alternative etiology exists.
Not Related	The event is due to an underlying or concurrent illness or effect of another drug and is not related to the study drug (e.g., has no temporal relationship to study drug or has a much more likely alternative etiology).

8.2.3 Expectedness

The Principal Investigator will be responsible for determining whether an AE is expected or unexpected. An AE will be considered unexpected if the nature, severity, or frequency of the event is not consistent with the risk information previously described for the study product.

8.3 Time period and frequency for event assessment and follow up

The Investigator will monitor each subject for clinical evidence of adverse events on a routine basis throughout the study. Any AE/SAE prior to the Baseline visit will be considered past medical history (PMH). The AE reporting period for this study begins upon receiving the first application of investigational product and ends at the final protocol required visit. SAE(s) that are observed or spontaneously reported during the subject's participation in the trial will be captured and monitored until the Investigator deems the event to be chronic or not clinically significant or the subject to be stable.

8.4 Reporting procedures

8.4.4 Adverse event reporting

8.4.4.1 *Serious adverse event reporting*

In the event of a SAE, whether related to study drug or not, the Investigator or representative must make an accurate and adequate report consisting of at least the minimum criteria (Site and Subject ID, Date site became aware of the event, SAE Term, Seriousness criteria, Study Drug information, Investigator/Reporter and site address) within 24 hours by email, or telephone to the Sponsor's (Alliance Pharmaceuticals Ltd) US-based Scientific Affairs Team

([contact], [contact].). Alliance Pharmaceuticals Ltd. Personnel will complete the SAE report onto a MedWatch 3500A form for evaluation and convey for review by the Medical Monitor and Site Investigator. Accurate Completion of the MedWatch 3500A form will consist of all data supplied such as Subject's demography, SAE narrative, concomitant medication, laboratory parameters and relevant medical history. In addition, if required by the applicable IRB/source document, the Investigator will submit the SAE reports to the IRB/source document within 15 calendar days of discovering the SAE, or alternatively, within accordance of applicable regulations or IRB/source document requirements.

Copies of each report with the associated documentation (i.e., queries, medical records, lab records, IRB communications and all source documents) will be kept in the site's study file.

A subject experiencing one or more SAEs will receive treatment and follow-up evaluations by the Investigator or may be referred to another appropriate physician for treatment and follow-up. The Investigational Site will be responsible for collection and forwarding follow-up SAE information to the Alliance Pharmaceuticals Scientific Affairs Team.

MEDICAL MONITOR
Alliance Pharmaceuticals Ltd.
E-mail: [contact]
Alliance Pharmaceuticals Ltd. [name], United Kingdom

8.4.5 Unanticipated problem reporting

All Serious and Unexpected Suspected Adverse Reactions (SUSAR) will be submitted as expedited reports to the applicable regulatory authorities/federal agencies.

8.4.6 Reporting of pregnancy

If a subject, or female partner of male subject becomes pregnant during the participation in the study, the Investigator will immediately discontinue the subject from the study and contact the Medical Monitor and the Sponsor. Diligent efforts will be made to determine the outcome for all pregnancy exposures in the clinical trial. Information on the status of the mother and the child will be forwarded to the Sponsor's Safety Team using the Pregnancy Data Collection Form. Generally, follow-up will occur within 6 to 8 weeks following the estimated delivery date. Any premature termination of the pregnancy will be reported. Detailed guidance on the reporting of Pregnancies will be provided in SAE and Pregnancy Reporting Guidance.

